#### 6.6 Intra-patient Dose Reduction and Escalation (Phase 1b Dose Optimization Part 4: DLT evaluation period)

Intra-patient dose reductions of TTI-621 are not permitted in the DLT evaluation period (Week 1-3) in the phase 1b dose optimization unless the patient experiences a DLT attributed to TTI-621. If a patient experiences a DLT during the first 21 days, treatment should be held and the event counted toward the assessment of MTD for the given cohort. These patients may continue in the study upon resolution of the toxicity at a reduced dose

level. Patients who receive a reduced dose of TTI-621 during the DLT evaluation period for reasons other than DLT will be replaced.

During phase 1b dose optimization, when the MTD or recommended phase 2 dose of TTI-621 is determined, all patients who have received TTI-621 at a dose lower than the recommended dose for a minimum of 4 weeks may dose escalate to the recommended dose in the absence of PD or unacceptable treatment-related toxicity at the investigator's discretion and with the medical monitor's approval. Patients for whom an increase in the dose of TTI-621 is being considered must have TEAEs resolve to  $\leq$ Grade 1 or baseline or to a level that is acceptable to the investigator (non-hematologic toxicity must be  $\leq$ Grade 2, hematologic toxicities must be recovered to levels above the minimum requirement for TTI-621 dosing).

## 6.7 Management of Clinical Events

### *Infusion-Related Reactions (IRR)*

Premedication with an antihistamine and acetaminophen is required for all subjects prior to infusion of TTI-621. During and immediately after infusion, patients will be closely monitored for signs and symptoms of allergic reactions. In the event of a reaction of any severity during the infusion itself, the infusion should be stopped and standard institutional supportive care administered.

Grade 1 or 2: If the reaction was Grade 1 or 2 in severity and the signs and symptoms have fully resolved, the infusion may be restarted. Any patient who experiences a Grade 2 allergic reaction must receive premedication with corticosteroids per standard institutional supportive care prior to receiving subsequent infusions.

Grade 3: If a patient experiences a Grade 3 IRR, the investigator may consider the following: 1) restarting the infusion after medical intervention and after the patient's condition has stabilized with additional supportive care medications, 2) terminating the current infusion, but re-challenging at the next weekly dose, or 3) permanently discontinuing the study treatment. When re-challenge occurs, the patient should receive pre-medication with corticosteroid per standard institutional practice, and a slower infusion rate and/or a reduced dose of TTI-621 should be considered. The investigator and medical monitor will decide to continue treating patients who experienced a Grade 3 IRR on a case-by-case basis. As with all AEs of special interest, the medical monitor should be apprised of any Grade 3 or higher infusion reaction that occurs during the study.

Grade 4: If the allergic reaction was Grade 4, the patient will be permanently discontinued from treatment.

### *Thrombocytopenia*

Blood counts should be monitored regularly as outlined in the protocol with additional testing obtained according to standard clinical practice. Administration of TTI-621 should be modified per dose modification guidance in the protocol when thrombocytopenia occurs (see [Section 6.5.3](#)). Platelet transfusion is allowed to manage severe thrombocytopenia to prevent and minimize bleeding according to the American Society of Hematology Transfusion guidelines or American Society Clinical Oncology platelet transfusion guideline. Per these guidelines, the platelet count threshold for prophylactic platelet transfusion is  $<10,000 \times 10^9/L$ . Investigators are advised to consider individual patients' bone marrow function, underlining disease, medical history, concomitant medication, and concurrent conditions and decide how to clinically manage thrombocytopenia.

## **6.8 Concomitant Medications and Treatment**

### **6.8.1 Required Concomitant Treatments**

All subjects must be premedicated with an antihistamine and acetaminophen prior to infusion of TTI-621. For subjects in the combination cohorts, premedication with an antihistamine and acetaminophen should be given prior to the combination agent infusion and must be repeated if the infusions of the combination agent and TTI-621 are separated by more than 4 hours.

### **6.8.2 Allowed Concomitant Treatments**

The Investigator is permitted to use standard supportive care for symptom control or drug-related toxicity; this might include analgesics, antiemetics, electrolyte replacement, topical steroids, hydration, and/or blood product transfusions. Other prescribed medications for non-neoplastic conditions are allowed, as well as vitamins and nutritional supplements. Chronic use of steroid above a daily equivalent dose of 20 mg prednisone is not permitted on study with the exception of CTCL patients who had been on a stable dose of medium or low-potency topical steroid for 4 weeks before the first dosing of the study drug. These patients can continue to use the same dose of topical steroid for symptom control on study.

Use of selected reversible anticoagulants (low molecular weight heparin, heparin, warfarin or dabigatran) for prevention or treatment of thrombosis is permitted per the

2017 National Comprehensive Cancer Network (NCCN) guidelines, “Cancer-Associated Venous Thromboembolic Disease”, with dose adjustments for thrombocytopenia per local institutional guidelines, with maintenance of platelet count  $>50 \times 10^9/L$  or per local institutional standard. Use of low dose aspirin ( $\leq 81 \text{ mg day}$ ) is permitted for control of malignant thrombocytosis.

Myeloid growth factors are permitted for rescue from treatment-emergent Grade 3 or 4 neutropenia. Likewise, erythropoiesis-stimulating or megakaryopoiesis-stimulating agents may be used for treatment-emergent anemia or thrombocytopenia, respectively.

Palliative radiotherapy of limited scope (ie, not exposing a significant amount of marrow) for the purpose of symptom relief may be permitted after consultation with the Medical Monitor and will not preclude continuation of TTI-621 administration.

### **6.8.3 Prohibited Concomitant Treatments**

No other systemic anticancer modalities (including cytotoxic, immunomodulatory, biological, ECP, topical anti-neoplastics or hormonal agents) or additional investigational agents are permitted with the following exceptions in the expansion phase only:

- In subjects with CTCL, chronic use of steroid above a daily equivalent dose of 20 mg prednisone is not permitted on study with the exception of CTCL patients who had been on a stable dose of medium or low-potency topical steroid for 4 weeks before the first dosing of the study drug. These patients can continue to use the same dose of topical steroid for symptom control on study.

Ongoing requirement for systemic corticosteroids of greater than 20 mg prednisone or equivalent is cause for exclusion at screening; the required initiation of corticosteroids during treatment (other than for treatment of an acute symptom) must be discussed with the Medical Monitor and tapered back to 20 mg prednisone or equivalent per day as soon as clinically feasible.

Use of irreversible anticoagulants is not permitted at any time during the study.

Requirement for surgery during treatment will occasion either TTI-621 treatment delay or discontinuation and will be handled case-by-case between the Investigator and Medical Monitor.

## 6.9 Removal of Subjects from Therapy or Assessment

Subjects will be counseled that they are free to withdraw from the study at any time. Over the course of the study, the Investigator and/or the Sponsor may withdraw a subject from treatment for any of the reasons listed below:

- disease progression (see [Section 7.14.1](#))
- unacceptable toxicity, including any treatment-emergent Grade 4 nonhematologic toxicity considered related to TTI-621
- intercurrent illness compromising ability to fulfill protocol requirements
- requirement for alternative treatment in the opinion of the Investigator
- significant noncompliance to protocol
- withdrawal of consent by the subject
- administrative reason (eg, termination of the study by the Sponsor)
- loss to follow-up
- death

The Sponsor should be notified of the withdrawal and its reason(s). When a subject withdraws from treatment, all safety data normally required at the end of the study (ie, the end-of-treatment visit, end of study, and safety follow-up) will be obtained if possible as outlined in [Sections 7.11–7.12](#).

## 7 TESTS AND EVALUATIONS

[figure not shown]
All required observations with their schedules are summarized in [Appendix D, Table 1](#) (Part 2 and 3) and [Appendix D, Table 2](#) (Part 4). Unless otherwise stated, the assessments below pertain to patients enrolled in both Part 3 and Part 4 of the study. Concomitant medications will be recorded from the time of informed consent through the safety follow-up visit. AEs will be recorded from the start of the first dose of study treatment through the safety follow-up visit (see [Section 9.4](#)).

Routine laboratory assessments, such as serum chemistries, hematology, coagulation and urinalysis, will be performed locally. In order to minimize required blood volume, pediatric tubes are suggested (but not required) for hematology and serum chemistries.

Special tests such as PK, ADA, and pharmacodynamic/biomarker samples will be performed centrally or as individually indicated. Additional information on the handling and processing of these samples may be found in the separate Laboratory Manual.

For subjects enrolled in the phase 1b expansion part of the study parts 2-4, there is a window of  $\pm$  2 days (2 days early or 2 days later) for any scheduled treatment days to permit holidays, travel, clinic scheduling and other delays from Week 2 and beyond. If the actual visit occurs greater than 2 days from the planned visit, that planned visit will be considered to have been missed and subjects should proceed with the next planned visit. All response assessments have an allowable window of  $\pm$  1 week. Fresh biopsies, photographs and TCR V $\beta$  whole blood collections also have a  $\pm$  1 week allowable window to align with response assessments.

CCI

### 7.1 Screening Period

Informed consent may be obtained within 30 days prior to Day 1, after which it is recommended that the subject be re-consented. The following procedures will be performed after written informed consent has been obtained and within 14 days prior to the planned start of treatment unless otherwise noted:

- physical examination including review of systems (breast/chest, extremities, head/ears/eyes/nose/throat, lymph nodes, musculoskeletal, pulmonary and skin), and height
- body weight

- ECOG performance status (see [Appendix B](#))
- vital signs including heart rate, respiratory rate, and body temperature
- baseline disease assessment as indicated for the specific primary malignancy (see [Section 7.14.1](#) and [Appendix D. Table 3](#)) within 28 days prior to the planned start of treatment. CTCL: mSWAT, CAILS (local disease only) and central photographs.
  - Leukemia and lymphoma with marrow involvement: bone marrow aspirate for routine morphology, flow cytometry, CD47 expression and receptor occupancy (not required for Part 4)
  - CTCL: photographs of tumor lesions will be captured at the clinical site(s) using standardized photographic equipment, methodologies and services provided by Canfield Scientific, Inc. (Parsippany, New Jersey). Further detail for study photography will be provided in the supplied Canfield User Manual
- CTCL and PTCL (Part 3 only): Radiographic disease assessments for CTCL and PTCL will be submitted for central review (central results are not required for enrollment). Please refer to the Imaging Manual. Part 4 will not require submission of scans for central review in real time but retrospective submissions might be requested by sponsor.
- CTCL and PTCL (Part 3 only): Tumor tissue will be submitted for central review for subjects with CTCL (not including SS) and PTCL to confirm the diagnosis (central disease confirmation not required for enrollment). For subjects with SS, peripheral blood is acceptable. Archival tissue may be provided. Refer to the Laboratory Manual for additional details.
- resting 12-lead ECG
- hepatitis B (HBsAg and HBcAb) and C (HCV Ab) panel
- serum pregnancy test for women of childbearing potential
- serum chemistries, including alkaline phosphatase, albumin, ALT, AST, bilirubin (direct, indirect, and total), blood urea nitrogen (BUN), creatinine, glucose, lactate dehydrogenase (LDH), total protein, uric acid, and electrolytes (sodium, potassium, calcium, chloride, bicarbonate, phosphorus)
- hematology, including WBC with 5-part automated differential, hemoglobin, RBC, absolute reticulocytes, platelets
- coagulation panel (prothrombin time, partial thromboplastin time, INR, and plasma fibrinogen)
- thyroid-stimulating hormone (TSH; only for subjects in the nivolumab combination cohort)
- Tumor tissue for biomarker analysis: fresh tumor biopsy tissue, if feasible, to be performed for all patients. If tumor biopsy is not feasible archival tissue is

acceptable. For subjects with SS, peripheral blood is acceptable, if a fresh biopsy is not possible. Refer to the Laboratory Manual for additional details.

The following complete historical subject information will be captured prior to Day 1:

- medical history
- history of malignancy, including histologic or cytologic confirmation of the primary malignancy, primary diagnosis date, prior treatments for the malignancy, and documentation of prior response and relapse status
- ongoing medications including those administered within 14 days prior to the planned start of treatment
- QOL via FACT-G questionnaire (all tumor types) and SKINDEX29 questionnaire (subjects with CTCL)

## 7.2 Day 1 Pre-infusion

For the TTI-621 monotherapy cohorts, the procedures listed below will be performed at the indicated time relative to the infusion of TTI-621. For subjects in the combination cohorts, the procedures below will be performed relative to the infusion of the combination partner. Except where noted, these assessments can be performed up to 24 hours pre-infusion. Baseline testing are assessments preformed within 3 days prior to or on Day 1 pre-dose. Subjects with screening laboratories within 3 days prior to dosing for a particular variable need not repeat the test on Day 1. To proceed with Day 1 infusion, subjects should meet eligibility criteria.

- symptom driven physical examination (as before) and ECOG score
- body weight
- vital signs prior to infusion (performed per the institutional standard of care)
- resting 12-lead ECG within 60 minutes prior to infusion ( $\pm$  30 minutes)
- serum chemistries (as before)
- hematology (as before)
- serum for PK 30 minutes pre-infusion (see [Section 7.14.2](#))
- biomarkers ( $\pm$  15 minutes; see Laboratory Manual for details of sample splitting, preparation, and shipping)
  - serum for cytokine/chemokine panel (not required for Part 4).
  - serum for anti-tumor antibodies (not required for Part 4).
  - whole blood TCR V $\beta$  sequencing (not required for Part 4).
  - whole blood for receptor occupancy

- whole blood for innate and adaptive response assay (not required for Part 4).
- serum for ADA prior to infusion ( $\pm$  15 minutes)
- urinalysis (color, appearance, specific gravity, pH, glucose, bilirubin, ketones, occult blood, protein)
- coagulation for Part 4 only

Subjects in the combination cohorts will also undergo the following additional assessments. These assessments are to be done after the combination partner infusion and prior to the TTI-621 infusion:

- vital signs 60 minutes ( $\pm$  15 minutes) after completion of the combination partner infusion (only if the combination partner and TTI-621 are administered more than 60 minutes apart); performed per the institutional standard of care
- vital signs prior to TTI-621 infusion ; performed per the institutional standard of care

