### 6.4.2 TTI-621 plus Rituximab Combination Cohort

Subjects enrolled in this cohort will receive a starting dose of 0.1 mg/kg TTI-621 in combination with 375 mg/m^2 rituximab given weekly (1 cycle) for up to 8 cycles according to the institutional standard of care. Intrasubject TTI-621 dose-

intensification is required for newly enrolled subjects as outlined in [Section 6.5.4](#). Subjects who complete 8 cycles of combination therapy or those who have unacceptable toxicity to the combination therapy prior to completion of 8 cycles may continue to receive TTI-621 as a single agent.

All subjects receiving the TTI-621 plus rituximab combination will have previously received rituximab and are thus less likely to experience the typical “first dose” infusion reactions upon re-exposure to rituximab. For subjects in this combination cohort, if rituximab is given on the same day as TTI-621, at least 60 minutes must elapse between completion of the rituximab infusion and initiation of the TTI-621 infusion. Rituximab may also be given the day before TTI-621 infusion, particularly for subjects who have a history of Grade 2 or 3 rituximab infusion-related reactions. Any rituximab infusion-related reactions must be Grade 2 or lower and have fully resolved to initiate the TTI-621 infusion on the same day. Any rituximab infusion-related reactions that do not meet these criteria must be discussed with the Medical Monitor to determine optimal next steps. Subjects who have had a prior Grade 4 rituximab infusion reaction will not be included in the combination TTI-621 plus rituximab cohort.

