#### **6.4.3 TTI-621 plus Nivolumab Combination Cohort**

Subjects enrolled in this cohort will receive a starting dose of 0.1 mg/kg/week TTI-621 in combination with nivolumab at 3mg/kg given every 2 weeks or a fixed dose per current FDA approved package insert for cHL. Intrasubject TTI-621 dose-intensification is required for newly enrolled subjects as outlined in [Section 6.5.4](#). Subjects who have unacceptable toxicity to nivolumab may continue to receive TTI-621 as a single agent.

For subjects in this combination cohort, if nivolumab is given on the same day as TTI-621, at least 60 minutes must elapse between completion of the nivolumab infusion and initiation of the TTI-621 infusion. Nivolumab may also be given the day before TTI-621 infusion. Any nivolumab infusion-related reactions must be Grade 2 or lower and have fully resolved to initiate the TTI-621 infusion on the same day. Any nivolumab infusion-related reactions that do not meet these criteria must be discussed with the Medical Monitor to determine optimal next steps.

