### **6.5.2 Criteria for Retreatment and Dose Delays**

TTI-621 is given as weekly infusions. Before each TTI-621 dose can be delivered, the patients' ANC must be  $\geq 1 \times 10^9/L$  and the platelet count must be  $\geq 75 \times 10^9/L$  or baseline. In addition, all other toxicity considered to be related to treatment with TTI-621 must have resolved to  $\leq$ Grade 1 or to the patient's baseline values with the exceptions listed below. If other AEs, not listed below, resolve to a level that is determined to be acceptable (and  $\leq$ Grade 2) for TTI-621, re-dosing is allowed based on a benefit-risk assessment by the investigator and medical monitor on a case by case basis. The decision will be documented.

Exceptions:

- Grade 2 gastrointestinal symptoms such as nausea, vomiting, and diarrhea that are easily treatable
- Grade 2 fatigue or other constitutional symptoms
- Grade 2 lymphopenia, neutropenia, and/or leukopenia in the absence of opportunistic infection
- Grade 2 thrombocytopenia in the absence of clinically meaningful bleeding
- Grade 2 anemia in the absence of shortness of breath and/or congestive heart failure
- Transient asymptomatic  $\leq$ Grade 3 laboratory abnormalities that is manageable with standard supportive care and considered not clinically significant following agreement between investigators and the sponsor or designees.

If the patient fails to meet the above-cited criteria for retreatment, initiation of the next dose of TTI-621 should be delayed for 1 week. At the end of that time, the patient should be re-evaluated to determine whether the criteria for retreatment have been met. If toxicity does not resolve by three weeks then the patient will be considered for removal from the study. If, in the opinion of the investigator and the medical monitor, it is in the patients' best interest to continue treatment with TTI-621 then the dose of TTI-621 should be reduced by at least 1 dose level after recovery of the toxicity or toxicities in question. In such circumstances, when a dose reduction of TTI-621 is required, no re-escalation of dose will be permitted.

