**Table 7-1: Week 1 Temporal Summary of Infusion and Post-infusion Assessments**

	T = 0 min	T + 60 min	T + 2 hr	T + 4 hr	T + 24 hr	T + 72 hr
Start TTI-621 infusion		Start infusion [Timeline: T = 0 to T + 60 min]	End infusion			
		- - - - - Monitor for infusion reactions - - - - -				
		Vital signs	Vital signs	Vital signs		
		ECG				
		Receptor occupancy				
		Pharmacokin.	Pharmacokin.	Pharmacokin.	Pharmacokin.	Pharmacokin. (Part 4 only)
		Hematology	Hematology	Hematology	Hematology	Hematology (Part 4 only)
		Cytokines/chemokines (Part 3 only)		Cytokines/chemokines (Part 3 only)		

## 7.4 Week 2

On Day 1 of Week 2 (Day 8 of treatment), the below tests and observations will be performed. For the TTI-621 monotherapy cohorts, assessments will be performed at the indicated time relative to the infusion of TTI-621. For subjects in the combination cohorts, assessments will be performed relative to the infusion of the combination partner, as applicable. All of these assessments can be performed up to 24 hours pre-infusion, with the exception of vital signs, PK, and biomarkers. Post-infusion procedures will be relative to the TTI-621 infusion.

- symptom-driven physical examination and ECOG score
- body weight
- vital signs prior to infusion and at completion of infusion (60 minutes after Time 0 [ $\pm$  15 minutes]). For subjects in the combination cohorts, the latter timepoint (60 minutes after Time 0) is to be done only if the combination partner and TTI-621 are administered more than 60 minutes apart; performed per the institutional standard of care. For subjects under Part 4, vitals are not required at end of infusion. Refer to [Appendix D. Table 2](#).
- biomarkers ( $\pm$  15 minutes; see Study Manual for details of sample splitting, preparation, and shipping):
  - serum for cytokine/chemokine panel (pre-dose), not required for Part 4
  - whole blood for receptor occupancy (pre-dose) for Part 3 and 4. For Part 4, if a priming dose is used see [Appendix F](#) for revised sampling timepoints.
- Serum for PK:
  - For Part 3 and Part 4: serum for PK trough levels (pre-dose). See [Appendix D. Table 1](#) and [Appendix D. Table 2](#). If a priming regimen is used, see [Appendix F](#) for revised sampling timepoints.
- Hematology:
  - For Part 3: pre-dose (results must be available prior to start of infusion). Further hematologic monitoring should be instituted at the discretion of the treating Investigator.

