## 7.10 Weeks 9 and Higher

### 7.10.1 Phase 1b Part 3

The following assessments are applicable for Part 3.

For subjects in the monotherapy cohorts, the procedures listed below will be performed at the indicated time relative to the infusion of TTI-621. For subjects in the combination cohorts, pre-infusion procedures will be relative to the combination agent infusion, where applicable. Post-infusion procedures will be relative to the TTI-621 infusion. All assessments can be performed up to 24 hours pre-infusion, with the exception of PK and biomarkers. The below testing intervals represent a minimum; subjects with an ongoing abnormality should be monitored more frequently as clinically indicated.

- symptom driven physical examination and ECOG score Day 1 of Week 12 and every 4 weeks thereafter
- vital signs, performed per the institutional standard of care
- body weight measured every other week (Week 10, 12, etc.). After Week 8, the weight taken at the prior visit may be used to calculate dose (e.g. weight at Week 8 used for Week 9 dosing)
- disease assessment (see [Appendix D. Table 3](#)) at the end of Weeks 16 and 24, followed by every 12 weeks (Weeks 36, etc.) or at the point that clinical progression is observed or suspected.
  - For CTCL and PTCL subjects, central submission of radiographic disease assessments is required.
  - CTCL subjects only: mSWAT, CAILS (if applicable) and photographs at time of disease assessments
  - Peripheral blood and blood smear for central pathology review for SS subjects only. Refer to the Laboratory Manual and to [Appendix D. Table 3](#) for additional details.
- Week 16 pre-infusion: fresh tumor sample from an identified target lesion for CTCL subjects only
- resting 12-lead ECG Day 1 of Weeks 16 and 24
- QOL by FACT-G (all subjects) and SKINDEX29 (CTCL only): post-dose on Week 16 and 24, and then every 12 weeks thereafter
- urine or serum pregnancy test for women of childbearing potential Day 1 of Week 12 and every 4 weeks thereafter
- serum chemistries Day 1 of Week 12 and every 4 weeks thereafter
- hematology Day 1 of every week (results must be available prior to start of infusion). Further hematologic monitoring should be instituted at the discretion of the treating investigator.

- serum for PK (see [Table 7-2](#)):
  - Day 1 of Week 9 and every week through Week 16 inclusive: trough level (pre-infusion)
- biomarkers ( $\pm$  15 minutes; see Study Manual for details of sample preparation and shipping):

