**Table 7-2: Summary of PK Sampling Times**

Week	Day	Nominal Time	Allowable Time Window
N	1	Pre-infusion (within 30 min)	± 15 min
	1	EOI (60 min) §	+5 min
	1	T + 2 hr §	± 15 min
	1	T + 4 hr §	± 15 min
N	2	T + 24 hr §	± 6 hrs
N	4	T + 72 hr §	± 24 hrs
N	1	trough (30 min pre-infusion)	± 15 min
EOT		Within 1 week following final dose	

EOI = immediately after the end of infusion (i.e., prior to flush)

EOT = end of treatment

N = any week where the listed timepoints are applicable

§ Relative to the start of first TTI-621 infusion

CCI

- CCI [REDACTED]  
[REDACTED]
- [REDACTED]  
[REDACTED]
- [REDACTED]  
[REDACTED]
- [REDACTED]  
[REDACTED]

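### At visits with a combination partner, TTI-621 trough and pre-dose receptor-occupancy samples are timed to the partner infusion, so troughs can be drawn up to about 24 hours early

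*Protocol*

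**What the plan says.** **Which infusion anchors the pre-dose samples.** Section 7.2 (Day 1) says: "For subjects in the combination cohorts, the procedures below will be performed relative to the infusion of the combination partner". Section 7.4 (Week 2) says: "For subjects in the combination cohorts, assessments will be performed relative to the infusion of the combination partner, as applicable". The same rule stands in Sections 7.5 to 7.8. For Weeks 9 and higher, Section 7.10 says that "pre-infusion procedures will be relative to the combination agent infusion", where applicable, and Section 7.9 (Week 8) is similar. Samples after dosing have the other anchor: "Post-infusion procedures will be relative to the TTI-621 infusion" (Section 7.4, repeated in 7.9 and 7.10).

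**When the partner may be given.** Section 6.4.2: "Rituximab may also be given the day before TTI-621 infusion". Section 6.4.3: "Nivolumab may also be given the day before TTI-621 infusion". On the same day, at least 60 minutes must separate the end of the partner infusion from the start of TTI-621.

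**What a trough is.** Section 7.14.2 puts it 30 minutes pre-dose. Table 7-2 lists "trough (30 min pre-infusion", with a window of ±15 minutes, and does not name the infusion. Its footnote tying times to TTI-621 is attached to the post-infusion rows only. Appendix D Table 1 marks these samples simply as pre.

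**What the count gates.** Section 6.5.2: "Before each TTI-621 dose can be delivered, the patients' ANC must be" above a threshold, with a platelet criterion alongside. It gives no maximum age for the sample.

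**What the SAP does.** Section 3.6.1 summarises concentrations at each time point and lists elapsed time and deviation from schedule. Section 3.6.2 uses actual sampling times for PK parameters.

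**The concern.** A trough describes TTI-621 just before the next TTI-621 dose. If it is timed to a partner infusion given the day before, the sample is taken while more drug is still present. It is nevertheless filed under the same nominal time point as a true trough. Sites that read Table 7-2 as meaning TTI-621 would sample at the right time, so the cohort summary would mix two sampling times. Pre-dose receptor occupancy has the same problem, and its paired end-of-infusion sample is timed to the other drug.

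PK and pharmacodynamics are secondary endpoints for these cohorts, which may enrol up to 40 (rituximab) and 15 (nivolumab) subjects. A second, separate matter is the blood count that gates each TTI-621 dose: the visit sections and Section 6.5.2 do not clearly refer to the same infusion.

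**Working it through.** The plan states no figure for this point, so there is none to reproduce. The check is arithmetic on its timing rules.

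**1. Visits affected.** Only those with a partner infusion. Rituximab is weekly for up to 8 cycles. Without delays, that covers the troughs of Weeks 2 to 8, or 7 per subject. Nivolumab may be every 2 weeks, so within one subject the anchor can alternate from week to week. Day 1 precedes any TTI-621 and has no trough.

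**2. Time of the sample.** The dosing interval is 7 × 24 = 168 h. Let g be the hours from the anchoring infusion to TTI-621.
- Anchored to TTI-621: 168 − 0.5 = 167.5 h after the previous dose.
- Partner the day before, read as g ≈ 24: 168 − 24 − 0.5 = 143.5 h.
- Partner the same day, with g assumed to be 2 to 5 h (partner infusion time plus the 60-minute gap): 165.5 to 162.5 h.

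**3. Effect on the trough.** Protocol Section 1.6.4 gives a terminal half-life of 35.2 to 156 h in monkeys; the documents give no human value. Assuming that range and mono-exponential decline, the overstatement factor is 2^(g / half-life).

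| g | half-life 35.2 h | half-life 156 h |
|---|---|---|
| 24 h | 2^(24/35.2) = 1.60 | 2^(24/156) = 1.11 |
| 5 h | 2^(5/35.2) = 1.10 | 2^(5/156) = 1.02 |
| 2 h | 2^(2/35.2) = 1.04 | 2^(2/156) = 1.01 |

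The day-before shift gives about 60% to 11%, and the same-day shift about 1% to 10%. Receptor occupancy cannot be quantified from the documents.

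**4. What the analysis removes.** Actual times protect the PK parameters. They do not protect the trough summaries in SAP 3.6.1, which group by time point and have no exclusion rule for off-window samples.

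**5. Before-and-after pairs.** The pre-dose sample precedes the partner and the post-dose sample follows TTI-621. Section 7.2 adds only vital signs between the two infusions. Such pairs occur mainly in Week 1, the dose-intensification weeks and Week 8.

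**6. Age of the gating count.** From Week 2, hematology may be drawn up to 24 h before the anchoring infusion. With the partner about 24 h before TTI-621, the maximum age is 24 + 24 = about 48 h. On Day 1, screening laboratories up to 3 days old are accepted, so the maximum is 3 × 24 + 24 = about 96 h. These are sums of two allowances, not expected values. Section 7.4 requires the result before the infusion starts, without saying which infusion.

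**The case against.** The strongest reply is that this is loose wording. The later sections qualify the partner anchor as applicable, Section 7.14.2 speaks of TTI-621 infusions, and pre-dose is naturally read as before TTI-621. A site reading it that way makes no error. That stands: the defect is a conflict between sections, and it need not appear at every site. But the qualifier is undefined, and nothing says which reading governs. Sections 7.4 to 7.10 also exempt PK from the 24-hour window, but that only keeps the sample close to the anchoring infusion; it does not change the anchor.

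The percentages are also open to attack. Section 1.6.4 calls the monkey half-lives extremely variable, and Section 1.6.3 reports strong binding to monkey red cells but very low binding to human ones. That stands too. The time shift follows from the text, while the size of the bias is illustrative.

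Sampling before the partner gives a baseline for the whole regimen. For cytokines this is a reasonable choice, and moving a single tube would lose that baseline.

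Three stronger inferences are tempting, and the documents do not support them.
- A reader might infer that the planned analyses credit partner-driven cytokine or platelet changes to TTI-621. The SAP's laboratory summaries are baseline-to-worst shifts, adverse-event relationship is recorded separately for each partner, and pharmacodynamic analysis is outside this SAP.
- A reader might infer that early troughs will be reported as a partner interaction. No formal PK comparison of combination with monotherapy is planned.
- A reader might connect the Grade 3 gastrointestinal bleed in Section 1.7 with an old blood count. Nothing in the documents links them.

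**Conclusion.** The point holds for TTI-621 trough PK and pre-dose receptor occupancy at partner visits. Read as written, Sections 7.4 to 7.10 conflict with Section 7.14.2 and Table 7-2, and the trough can be up to about 24 h early, or a few hours early with same-day dosing. The overstatement of about 60% to 11% (day before) or 1% to 10% (same day) rests on monkey half-lives, mono-exponential decline, a day-before gap of about 24 h and assumed same-day gaps of 2 to 5 h. PK parameters computed from actual times are largely protected; trough summaries by time point are not.

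It would go too far to say that every pre-dose test is misplaced: vital signs are repeated before TTI-621, Week 3 has no cytokine or receptor-occupancy draw for these cohorts outside dose intensification, and visits without a partner are unaffected. On the gating count, the documents support only the finding that the passages need reconciling.

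**What to change.** 1. **Protocol 7.4 to 7.10, with a footnote to Appendix D Table 1.** State that in the combination cohorts TTI-621 trough PK and pre-dose receptor-occupancy samples are timed to the TTI-621 infusion, with the Table 7-2 window for PK (30 ± 15 minutes, so 15 to 45 minutes before TTI-621).
2. **SAP 3.6.1.** Exclude from trough summaries any sample outside that window before TTI-621. Keep it in the listings and, with its actual time, in the parameter calculations. The sponsor performs the PK analysis separately (SAP 3.6), so the rule should be carried into that work.
3. **Cytokines and platelets.** Leave the cytokine baseline relative to the partner. Note in the report that before-and-after cytokine and platelet changes in these cohorts reflect the regimen, not TTI-621 alone.
4. **Gating hematology.** Reconcile Sections 7.2 to 7.10 with Section 6.5.2 on which infusion the count refers to. No limit on its age is proposed here.

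The cost of items 1 and 2 is schedule wording, some coordination at sites between the two infusions, and a few samples lost from trough summaries. No extra tubes are needed.
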